After completion of 4 cycles of therapy, subjects will be evaluated every 6-9 weeks with radiologic imaging of the body (CT) and CNS (MRI) to assess response to treatment both inside and outside of the CNS. Response assessments will be completed by a radiologist at the treating site, findings will be confirmed by an independent radiologist, and evaluated by RECIST 1.1 criteria and immune-related criteria (irRC) for systemic disease, and MRI criteria for CNS disease. Following the first radiologic assessment of the body that demonstrates radiologic progressive disease (PD), RECIST 1.1 will be adapted as described in section 6.1.2.7.5 (Table 9) to accommodate for the tumor response patterns seen with pembrolizumab treatment (e.g., tumor flare) using immune-related RECIST criteria. Contrast-enhanced MRI Brain scans will be used to assess for measurable disease in the CNS at the time of screening, and to determine CNS radiologic response during the study. CNS radiologic response by MRI will be defined as a reduction in size of a measurable lesion throughout the neuro-axis, where a measurable lesion will be defined as one that is greater than or equal to 3mm in size, as detailed in section 6.1.2.7. CNS cytologic response will be assessed by two serial CSF cytology samples, as detailed in the section 6.1.2.8.3. Clinical response will be evaluated by the treating investigator, detailed in section 6.1.2.7 (Table 8).

[figure not shown]
After completion of 4 cycles of therapy or the patient's last dose of therapy, each subject will be followed for 90 days after the end of treatment for adverse event monitoring, or 30 days after the end of treatment if the subject initiates new anti-cancer therapy. Subjects who discontinue treatment for reasons other than PD will have post-treatment follow-up for disease status until PD, initiation of a new cancer therapy, withdrawal of consent, or becoming lost to follow-up. All subjects will be followed by telephone contact for overall survival (OS) until death, withdrawal of consent or the Investigator is notified by the Sponsor to discontinue follow-up, whichever comes first.

This trial will be conducted in conformance with Good Clinical Practices.

Specific procedures to be performed during the trial, as well as their prescribed times and associated visit windows, are outlined in the Trial Flow Chart – Section 5.0 Details of each procedure are provided in Trial Procedures- Section 6.0.

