4.1.5.1 Efficacy Endpoints

4.1.5.1.1 Primary Endpoint:

The primary efficacy endpoint is to evaluate CNS response with pembrolizumab in patients with LMD from solid tumors. CNS response will be defined either as radiologic response, cytologic response, or clinical response, whichever is easier to assess. Radiologic response will be defined as a reduction in size of a measurable lesion on a contrast-enhanced MRI scan of the brain. Cytologic response will be defined as a negative CSF cytology result in 2 consecutive samples, in patients who have initial positive cytology prior to treatment, or a clinical response, defined as an improvement in objective neurologic signs or symptoms attributable to LMD (Table 8). Response assessment is detailed in section 6.1.2.7.

4.1.5.1.2 Secondary Endpoints:

- **1. CNS Progression-free Survival:** A secondary endpoint of this study is to evaluate CNS-PFS, which will be defined as the time from study enrollment until CNS progression (radiologic, cytologic or clinical), or death, whichever occurs first. CNS progression will be classified as radiologic (determined by contrast-enhanced MRI scan), cytologic (determined by pathologic assessment of CSF cytology including cell count, differential, glucose) or clinical progression (defined as new objective neurologic signs or symptoms, attributable to LMD), as detailed in section 6.1.2.7.
- 2. **Overall Survival:** A secondary endpoint of this study is to evaluate OS, which will be defined as the time from study enrollment until death from any cause. Deaths from progressive disease will be stratified as related to CNS progression, related to systemic progression, or both.

8A

3. **Safety:** Safety will be evaluated according to the National Cancer Institute Common Terminology Criteria for Adverse Events (NCI CTCAE) version 4.0^{27} safety will be determined by the number of treatment-related toxicities of > grade 3 severity by CTCAE Version 4.0.

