6.1.2.7 Tumor Imaging and Assessment of Response

Evaluation of response will include an evaluation of neurologic signs and symptoms (normal, improved, stable, deteriorated), CSF obtained from a previous positive site (lumbar or ventricular), and repeated radiologic evaluation of all ancillary studies (MRI Brain and Total spine with gadolinium contrast enhancement and CT scans of the body). Patients will be evaluated for CNS response based on a 4-point scale: complete response, improvement, stable disease and progression, as detailed in the Table below:

Table 8: Determination of Response to LMD

Clinical Assessment (Neurologic Function)	Size of LMD disease on MRI or CSF cytology	Overall Response Determination
No neurologic symptoms	None detectable	Complete response

Improved	Stable	Improved
Stable	Improved	Improved
Stable	Stable	Stable
Improved	Progression	Progression
Stable	Progression	Progression
Progression	Improved or Stable	Progression

We will define a positive CSF cytology result either detectable malignant cells in the CSF, or a pathology read that is reported as "suspicious for malignancy." We will define a negative CSF cytology result as either no detectable malignant cells in CSF, or a pathology read of "abnormal CSF cytology response," which will indicate conversion from positive/suspicious to negative/abnormal CSF cytology^{31,32}.

A complete responder will be defined as a patient with a normal neurologic examination, negative CSF cytology and no measurable leptomeningeal masses on radiologic imaging. Improved patients will be defined as those that have demonstrated improvement in neurologic signs or symptoms and/or a 50% decrease in CSF tumor cells or persistent positive CSF cytology as defined above, a 50% shrinkage in the bidirectional measurements of leptomeningeal disease. Patients with stable disease will be defined as less than 50% improvement in number of CSF tumor cells or abnormal CSF cytology response as defined above, or reduction in size of LMD on radiologic assessment, without evidence of progression. Progression will be defined as more than 25% increase in the number of tumor cells or persistent positive CSF cytology as defined above, an increase in size of LMD masses on radiologic assessment, or the development of new neurologic signs or symptoms after at least 2 cycles of pembrolizumab therapy.

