7.2.4 Primary Efficacy Endpoint

CNS response

CNS response rate is defined as the proportion of the subjects in the analysis population who have a radiologic reduction in size of measurable CNS tumor lesions on an MRI brain scan, develop clearance of positive CSF cytology on 2 consecutive CSF specimens after an initial positive specimen has been obtained, or an improvement in neurologic function, as detailed in Table 8. In patients with more than one available response criterion, the most easily assessable criterion will be used.

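### The primary CNS response has no no-progression condition, so a patient whom Table 8 classes as progressed can be a primary responder and a CNS-PFS event at the same assessment

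*Combined protocol and SAP*

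**What the plan says.** **Primary endpoint.** Section 7.2.4 lists three routes to a response: smaller measurable lesions on MRI, clearance of positive cytology on two consecutive specimens, "or an improvement in neurologic function, as detailed in Table 8". It adds: "In patients with more than one available response criterion, the most easily assessable criterion will be used". Section 4.1.5.1.1 agrees: "CNS response will be defined either as radiologic response, cytologic response, or clinical response, whichever is easier to assess". Table 12 and section 7.2.1 set the assessment at 12 weeks, after 4 cycles.

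**Radiologic limb.** Section 2.1 says "CNS radiologic response by MRI will be defined as a reduction in size of a measurable lesion throughout the neuro-axis". Section 4.1.5.1.1 says "Radiologic response will be defined as a reduction in size of a measurable lesion on a contrast-enhanced MRI scan of the brain". Neither sets a minimum reduction or a condition on other lesions. Section 7.2.4 uses the plural, lesions, also without a threshold.

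**Table 8 (section 6.1.2.7).** The table has one clinical column, one combined MRI-or-cytology column, and an overall determination. One row reads "Improved Progression Progression": clinically improved, MRI or CSF progressed, overall progression. Another pairs clinical progression with MRI or CSF "Improved or Stable", and the overall result is again progression. The text below the table asks for 50% shrinkage for Improved, places smaller reductions under stable disease, and treats growth of LMD masses as progression.

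**CNS-PFS.** Section 4.1.5.1.2 counts radiologic, cytologic or clinical progression, or death. Section 7.2.5 refers to section 6.1.2.7 and Table 8.

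**The concern.** The primary endpoint and the first secondary endpoint use the same MRI, CSF and neurologic findings under incompatible rules. A patient whose symptoms improve while LMD grows, or whose CSF clears while neurologic function worsens, can enter the primary numerator and have a CNS-PFS event on the same date. Within MRI alone, one lesion may shrink while another grows.

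The trial is single-arm and open-label, with no formal inference, so its main efficacy statement is a proportion with an exact interval on about 16 patients. Who counts as a responder then determines the result. Letting the easiest criterion stand for the patient also leaves a choice that can be made after the outcomes are known.

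**Working it through.** **1. The plan's own figures.** 16/(1 − 0.10) = 17.8, rounded up to 18, as stated. The 90% Clopper-Pearson limits at N=16 reproduce for 1 to 5 responders (for example 3/16: 5.3% to 41.7%; 4/16: 9.0% to 48.4%). For 6/16 the lower limit of 17.8% reproduces. The upper limit computes to 60.9%, where the plan prints 60.1%; that does not bear on this point.

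**2. Both rules on the same patients.** Cross the two Table 8 columns, each Improved, Stable or Progression. Of the 9 cells, 5 contain an improvement and so can be a response under the any-one-domain wording:

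| Clinical | MRI/CSF | Section 7.2.4 | Table 8 |
|---|---|---|---|
| Improved | Improved | Response | Improved (row not printed; inferred) |
| Improved | Stable | Response | Improved |
| Stable | Improved | Response | Improved |
| Improved | Progression | Response | **Progression** |
| Progression | Improved | Response | **Progression** |

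Two of the five conflict. Both are also CNS-PFS events at that assessment.

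**3. Lesion level.** Under sections 2.1 and 4.1.5.1.1, shrinkage of one lesion by any amount suffices. Under section 6.1.2.7, a reduction below 50% is stable disease, and growth of LMD masses is progression.

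**4. Weight of one patient.** 1/16 = 6.25 percentage points.

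**5. Chance that it arises.** The documents give no discordance rate d. The expected number is 16d, and the chance of at least one is 1 − (1 − d)^16. For assumed d of 5%, 10% and 20%, the expected number is 0.8, 1.6 and 3.2, and the chance of at least one is 56%, 81% and 97%.

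**6. Gap between the any-domain rule and the same rule with a no-progression condition.** Assume that each assessable domain is improved with probability 0.15 and progressed with probability 0.30, with a common latent normal correlation. With independent domains the result is exact:

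- Three domains: any improved = 1 − 0.85³ = 38.6%. Improved with none progressed = 0.70³ − 0.55³ = 17.7%. Gap = 16 × 0.2093 = 3.3 patients.
- Two domains: 1 − 0.85² = 27.75%; 0.70² − 0.55² = 18.75%. Gap = 16 × 0.09 = 1.4 patients.

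With correlated domains (simulation):

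| Domains | Correlation | Any-domain | With condition | Gap, of 16 |
|---|---|---|---|---|
| 3 | 0.3 | 34.1% | 23.3% | 1.7 |
| 3 | 0.6 | 28.9% | 25.8% | 0.5 |
| 2 | 0.3 | 25.9% | 21.3% | 0.7 |
| 2 | 0.6 | 23.3% | 22.1% | 0.2 |

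With 10% improved and 25% progressed, three domains and correlation 0.6, the gap is 0.16 patients.

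**The case against.** The strongest defence is that section 6.1.2.7 was meant to govern. It says CNS response is evaluated on a 4-point scale, Table 8 has an overall determination column, and sections 2.1 and 4.1.5.1.1 both send the reader to 6.1.2.7 for response assessment. On that reading the override already applies and the fault is loose cross-referencing.

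This shows what may have been intended, but it does not settle the rule. No section says which of the four categories count as a response. The reference to Table 8 in section 7.2.4 follows the neurologic limb. Even if it binds that limb, MRI or CSF improvement with neurologic progression still conflicts. The easiest-criterion sentence points to one domain rather than a combined determination, and the 50% threshold does not fit the any-reduction wording.

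Several counterpoints stand and limit the claim:

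- A reader might infer that the plan inflates the response rate by a known amount. It does not follow. Scoring a single criterion chosen without regard to outcome would give 15% under the assumptions above, below the 17.7% to 25.8% for three domains with the condition. Inflation needs any-of-three scoring or an outcome-driven choice of criterion.
- A reader might contrast 6/16 with 3/16. That needs zero correlation and three assessable domains in every patient. Eligibility requires only MRI or cytologic disease, and cytologic response requires positive baseline cytology.
- A reader might infer that the endpoint has no time point, so that improvement at week 6 followed by progression counts. Table 12 and section 7.2.1 set 12 weeks, and a response followed by later progression is not in itself a contradiction.
- The response rate is not the only output: CNS-PFS, OS, safety and biomarkers are also planned.
- The single-lesion wording is in sections 2.1 and 4.1.5.1.1; section 7.2.4 uses the plural.

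**Conclusion.** The concern holds as a conflict between definitions at a single assessment. As written, sections 7.2.4 and 4.1.5.1.1 allow a primary response in a patient whom Table 8 classes as progressed and whom CNS-PFS counts as an event. The radiologic threshold also differs between sections.

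That conclusion rests on the text alone. The size does not: with no discordance rate in the documents, only the 6.25 points per reclassified patient is fixed. The ranges of 0.5 to 3.3 patients of 16 (three domains) and 0.2 to 1.4 (two domains), for correlation 0.6 down to 0, depend on the assumed 15% and 30% and on any-domain scoring. The effect could be negligible if the domains move together. The definition should still be settled before any patient is classified.

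**What to change.** 1. In section 7.2.4, define a responder for the analysis as a patient with improvement in at least one assessed domain and no progression, as defined in section 6.1.2.7, in any other assessed domain at the 12-week assessment.
2. Delete the easiest-criterion sentence from section 7.2.4 and the matching phrase from section 4.1.5.1.1. Otherwise the new definition would contradict them.
3. Judge radiologic response on all measurable LMD lesions recorded at baseline, with no new LMD lesion. Reconcile the any-reduction wording with the 50% wording in section 6.1.2.7.
4. Make the progression text usable for this purpose: section 6.1.2.7 lists persistently positive cytology under both Improved and Progression, so the condition in item 1 cannot yet be applied cleanly to CSF.
5. Report each domain separately beside the composite.

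Table 8 also feeds the discontinuation criteria in section 4.9. This proposal concerns only the analysis definition and leaves the table's role in treatment decisions unchanged. Sections 4.9, 6.1.2.7 and 7.2.4 must be reconciled with one another.

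The cost is wording in the SAP and the matching protocol sections. The MRI, CSF and neurologic assessments are already scheduled and N is unaffected. The downside is that the reported response rate may be lower.

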2.0 TRIAL DESIGN

2.1 Trial Design

This is an open-label phase II study of pembrolizumab in patients with advanced solid tumors with leptomeningeal carcinomatosis (LMD). Patients may have received any number of prior therapies for their respective solid tumors, but must not have received prior anti-PD-1 therapy and developed progressive disease. Approximately 18 subjects in this study will receive pembrolizumab at a dose of 200mg intravenously (IV) every 3 weeks (Q3W) for 4 doses. In patients who derive clinical benefit from therapy, pembrolizumab may be continued until documented disease progression, unacceptable adverse event(s), intercurrent illness that prevents further administration of treatment, investigator's decision to withdraw the subject, subject withdrawal of consent, noncompliance with trial treatment or procedure requirements, or for administrative reasons.

This study aims to determine if pembrolizumab can cause a radiologic, cytologic or clinical response in the CNS in patients with advanced solid tumors with LMD. The primary endpoint is thus central nervous system (CNS) response, defined either as radiologic response (reduction in size of LMD on gadolinium-enhanced MRI imaging of the brain and total spine including T1- weighted, T2-weighted, fluid attenuated inversion recovery and post-gadolinium sequences)

and/or cytologic response (conversion of positive to negative CSF cytology on 2 consecutive samples) and/or clinical response (Table 8), as detailed in the section 4.1.5.1.1 and 6.1.2.7.

Secondary endpoints will include progression-free survival (PFS), overall survival (OS), and safety.

Patients will undergo routine screening investigations including CBC, CMP, urine, pregnancy test, standard radiologic imaging of the body (CT), cerebrospinal fluid (CSF) sampling for cytology, and a pre-treatment gadolinium-enhanced MRI scan of the brain and total-spine. During the trial, patients will be monitored with a clinical visit, adverse event assessment and routine laboratory tests at the time of each dose of pembrolizumab. Patients will have a CSF sample taken, blood draws, radiologic imaging of the body (CT), and a contrast-enhanced MRI scan of the brain and total-spine after 2 and 4 cycles of therapy for response assessment and correlative studies. In patients with a CSF sample that demonstrates negative cytology, an additional confirmatory CSF sample will be obtained 3 weeks after the first negative CSF cytology sample.

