6.1.2.7.1. Initial Tumor Imaging

Initial tumor imaging and screening should be performed within 28 days prior to the date of allocation. The site study team must review screening images to confirm the subject is assessable for response based on MRI, CSF cytology or clinical presentation, as detailed in Table 8.

Tumor imaging performed as part of routine clinical management are acceptable for use as initial tumor imaging if they are of diagnostic quality, include all anatomy as described in the SIM, and performed within 28 days of the date of allocation.

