7. STATISTICAL ANALYSIS PLAN

7.1. Statistical Analysis Plan Summary

Key elements of the statistical plan are summarized in Table 12 below. A comprehensive plan is detailed in section 7.2

Table 12: Statistical Overview

Study Design Overview	Open-label, single arm phase II study of pembrolizumab in patients with advanced solid tumors with leptomeningeal carcinomatosis (LMD)
Treatment Assignment	pembrolizumab 200mg Q3W
Analysis Population	Eligible patients who receive at least one dose of pembrolizumab
Primary Endpoint	CNS response at 12 weeks based on either radiologic, cytologic or clinical evidence
Statistical Methods for Key Efficacy Analyses	The proportion of CNS response and associated 95% exact confidence interval will be provided
Statistical Methods for	Descriptive analysis based on Clopper-Pearson's exact binomial confidence interval method.
Key Safety Analyses	
Multiplicity	N.A.
Sample Size and Power	No formal statistical inference will be provided. The proposed sample size will provide appropriate estimation precision for the primary efficacy endpoint.

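### The primary CNS response is defined both as response in any domain and as response on one undefined, most easily assessed domain, and nothing fixes that choice before results are known

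*Combined protocol and SAP*

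**What the plan says.** Several places in the combined protocol and SAP define the primary endpoint.

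- **Any domain.** Section 2.1 (Trial Design) lists radiologic response "and/or cytologic response (conversion of positive to negative CSF cytology on 2 consecutive samples) and/or clinical response (Table 8"). The first sentence of 7.2.4 also joins the three domains with or.
- **One selected domain.** The second sentence of 7.2.4 reads: "In patients with more than one available response criterion, the most easily assessable criterion will be used". Section 4.1.5.1.1 reads: "CNS response will be defined either as radiologic response, cytologic response, or clinical response, whichever is easier to assess".
- **Either reading.** Table 12 in section 7.1 has "CNS response at 12 weeks based on either radiologic, cytologic or clinical evidence". This wording is compatible with both rules.

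The closest the documents come to a baseline rule is 6.1.2.7.1, where the site reviews screening images to "confirm the subject is assessable for response based on MRI, CSF cytology or clinical presentation". That checks that some domain can be assessed. It does not choose or record one.

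On assessors, 2.1 has radiology findings confirmed by an independent radiologist, but "Clinical response will be evaluated by the treating investigator". The trial is open-label.

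**The concern.** The two rules agree when a patient has only one available criterion, or when all available criteria agree. They differ when a patient responds in one available domain and not in another: the any-domain rule calls that patient a responder, while the selection rule follows whichever domain was judged easier. Because ease of assessment is undefined and no time of choice is set, two people applying the plan correctly to the same data can report different response rates.

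The CNS response rate is the only primary result of a single-arm, estimation-only trial, so its definition carries most of the weight. The domains are also not equally protected: imaging has independent confirmation and clinical response does not. Section 4.1.4.4 itself warns that varied response definitions make historical response rates in this disease hard to interpret, and an unsettled definition here would add to that difficulty.

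**Working it through.** **Inputs.** N = 16 analysable patients, defined as eligible patients who receive at least one dose (7.2.1). Intervals are Clopper-Pearson (7.2.1), at 90% in the sample-size table (7.2.1) and 95% for the analysis (Table 12).

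**Formula.** For x responders of n, the lower limit is the α/2 quantile of Beta(x, n−x+1) and the upper limit is the 1−α/2 quantile of Beta(x+1, n−x).

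**The plan's own figures.** At 90%, 2/16 gives 2.27 to 34.38 (printed 2.3 to 34.4) and 4/16 gives 9.03 to 48.44 (printed 9.0 to 48.4). These rows reproduce. The sample size also reproduces: 16/0.9 = 17.8, rounded up to 18.

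**Effect of the rule.** Hold the definition of response within each domain fixed, and let

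- a = patients who respond whichever available domain is used (including responders with only one available domain);
- b = patients with more than one available domain who respond in at least one but not in all.

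The any-domain count is a + b. The selection-rule count lies anywhere from a to a + b, depending on the domains chosen. It can therefore equal the any-domain count or fall below it, but cannot exceed it. The largest possible gap is b/16, which is 1/16 = 6.25 percentage points per patient.

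The documents give no discordance rates, so a and b are assumptions. With a = 2:

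| b | Selection rule, lowest | Any-domain rule (95% CI) | Largest gap |
|---|---|---|---|
| 0 | 2/16 = 12.5% | 2/16 = 12.5% (1.6 to 38.3) | 0 |
| 1 | 2/16 = 12.5% | 3/16 = 18.8% (4.0 to 45.6) | 6.25 points |
| 2 | 2/16 = 12.5% | 4/16 = 25.0% (7.3 to 52.4) | 12.5 points |
| 3 | 2/16 = 12.5% | 5/16 = 31.3% (11.0 to 58.7) | 18.75 points |

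**Why no Table 8 rate is given.** Section 6.1.2.7 says: "Patients will be evaluated for CNS response based on a 4-point scale: complete response, improvement, stable disease and progression". In that grid, progression in one column overrides improvement in the other, which could lower the count. The text below the grid also uses different thresholds:

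- It asks for 50% shrinkage, whereas 2.1 says: "CNS radiologic response by MRI will be defined as a reduction in size of a measurable lesion throughout the neuro-axis". A smaller shrinkage could count in 2.1 and not here.
- It allows improvement on a 50% fall in CSF tumour cells, with no conversion to negative cytology. Sections 2.1, 4.1.5.1.1 and 7.2.4 require two consecutive negative samples, so such a patient could count here and not there.

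A Table 8 count could thus be lower or higher than the any-domain count.

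**The case against.** The strongest reply is that the trial makes no formal inference and has no success threshold, so no decision turns on the rule, and that any numerical harm rests on assumed discordance. Both statements are true. They limit the consequence to the estimate, but the estimate is what this trial sets out to deliver.

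A second reply is that the selection sentence only deals with missing domains. It does not: it applies expressly where more than one criterion is available. It is fair to add that 4.2.6 admits patients on an MRI lesion or on cytology alone, so not every patient need be affected. The size of the affected group cannot be known from the documents.

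Third, any-domain scoring has its own cost. A patient with progression in another domain can count as a primary responder while also having a CNS-PFS event (4.1.5.1.2, 7.2.5). This stands, and is a reason to report that number and to leave the final rule to the sponsor.

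A reader might draw stronger conclusions that the documents do not support:

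- *That domains are meant to be chosen after results are seen.* The text does not prevent this, but nothing shows that it is intended.
- *That the selection rule inflates the rate above the any-domain rate.* It cannot, as the count above shows.
- *That Table 12 contradicts the selection rule.* Its wording fits both readings; the conflict rests on 2.1 and the first sentence of 7.2.4.
- *That Table 8 supplies a third, lower rate.* Its thresholds differ in both directions, so no such rate follows.

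**Conclusion.** The concern holds. The primary endpoint has two incompatible scoring rules for patients with more than one available criterion, and the selection rule is too undefined to be applied reproducibly. The effect is up to 6.25 points for each patient who responds in some available domains but not all. In the assumed case of two clear responders and two such patients, the reported rate can lie anywhere from 12.5% to 25.0%. If no patient is discordant, the two rules give the same rate.

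The result rests on N = 16, on the assumed counts, and on the same within-domain definitions under both rules. It concerns the estimate and its interpretation, not an error rate or the sample size. It should be settled before outcome data are reviewed.

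**What to change.** 1. Delete the selection sentence in 7.2.4 and the ease-of-assessment phrase in 4.1.5.1.1.
2. Score every assessed domain in every patient, and keep all eligible treated patients in the denominator, as Table 12 and 7.2.1 already provide.
3. Before outcome data are reviewed, state one governing rule in the same words in 2.1, 4.1.5.1.1, Table 12 and 7.2.4. The any-domain rule is what remains after the deletion. The sponsor may instead choose a Table 8 overall determination, if it first says which categories count as response.
4. Report radiologic, cytologic and clinical response separately, and the number of responders with progression in another domain.

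The chosen rule can be applied in only one way once the sponsor has also reconciled three points:

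- the radiologic threshold (any reduction in 2.1, 4.1.5.1.1 and 7.2.4; 50% in 6.1.2.7);
- the imaging field (brain MRI in 4.1.5.1.1 and 7.2.4; brain and spine, or the neuro-axis, in 2.1, while 4.2.6 admits a lesion on either brain or spine MRI);
- the cytology wording in 6.1.2.7, where an abnormal read is defined as negative but also listed under stable disease, and persistent positive cytology appears under both improvement and progression.

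Table 8 also drives discontinuation (4.9), so these passages are for the sponsor to reconcile and no category is proposed here.

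**Cost.** The endpoint wording needs only a short amendment; reconciling 6.1.2.7 takes more care because of its link to discontinuation. The sample size and the scheduled assessments do not change. Clinical response remains an unblinded judgement under either rule.
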